Effect of Transcranial Direct Current Stimulation on the Voice

Document date: 07/15/2024

Study protocol

The present study was approved by the Research Ethics Committee of the institution where the research was conducted (n. 5.758.856). All included volunteers signed the written informed consent prior to the experiment.

Vocally healthy individuals were recruited from the university community. We included volunteers of both sexes, aged 18 to 45 years, who scored up to 16 points on the Vocal Symptoms Scale (VSS), Brazilian version. The Brazilian Dysphonia Screening Tool (Br-DST) was also applied, and those who answered "yes" to both questions would be excluded.

Through a crossover study design, the volunteers underwent four experimental sessions separated by 7 days-minimum washout period to prevent cumulative effects of stimulations. In each session, a single target area was stimulated: (i) left laryngeal M1, (ii) left S1 of the larynx, (iii) left DLPFC, and (iv) cerebellum. The order of sessions was randomized in order counterbalanced by an external researcher to ensure blinding of both volunteer and therapist during vocal assessment. The allocation of sessions was securely concealed within opaque, sealed envelopes that were accessible only to the researcher responsible for tDCS.

The electrode setup during the tDCS sessions was as follows: (i) For left laryngeal M1, the anode was positioned over C5 (international 10-20 EEG system) and the cathode over the contralateral supraorbital region; (ii) For the left S1 of the larynx, the anode was positioned 3 cm posterior to C5 and the cathode over the contralateral supraorbital region; (iii) For left DLPFC, the anode was positioned over F3 and the cathode over the contralateral supraorbital region; (iv) For the cerebellum, the anode was placed over inion and the cathode over the right deltoid muscle. During the tDCS session, volunteers were instructed to sit in a chair and find a comfortable position. tDCS was delivered by an electrical stimulator (Neuroconn, Germany) through a pair of saline-soaked sponge electrodes (35 cm²) with a current intensity of 2mA for 20 minutes.

Before and after each session, volunteers were systematically evaluated for vocal acoustic parameters and laryngeal diadochokinesis. The vocal assessment analysis was performed immediately before and after tDCS using the Voxmetria and Vocalgrama software from CTS Informatics. Voice recordings were conducted using an HP Notebook Acer Aspire 5 PC with a Karsect HT-2° headset microphone and Andrea PureAudio™ USB-AS sound signal amplifier equipment. The microphone was positioned four centimeters away from the mouth at a

45-degree angle, with the participant seated and hands resting on their legs, forming a 90-degree angle.

The following tasks were requested: (i) Evaluation of vocal quality through sustained vowel / ϵ / for 5 seconds at weak intensity (below 70dB), habitual intensity (between 70 and 80dB), and strong intensity (above 80dB), controlled with a decibel meter. (ii) Cepstral analysis with sustained vowel / ϵ / for 5 seconds and the phrase "olha lá o avião azul" at weak, habitual, and strong intensities (as defined above), controlled with a decibel meter. (iii) Diadochokinesis assessment with the task of emitting vowels /a/ and /i/ separately, with rapid and interrupted repetitions of each vowel as fast as possible for eight seconds. (iv) Pitch range assessment through ascending and descending glissandos up to the maximum vocal extension in weak and strong emissions. (v) Assessment of reported vocal effort with sustained vocal effort emission. For phase 1, participants were asked to reproduce a note using a virtual keyboard (3 tones below their maximum glissando frequency) and then maintain that tone while counting from 21 to 30. Immediately afterwards, the participants answered the Adapted Borg CR10 for Vocal Effort Ratings (BR)¹⁷. Like the original protocol, the Adapted Borg CR10 for Vocal Effort Ratings (BR) maintained a scale from 0 to 10, where 0 means "no vocal effort at all", and 10 "maximum vocal effort".

For Vocal range profile, the participants were instructed to produce ascending (from low to high) and descending (from high to low) glissandos of the vowel / ϵ / as weak as possible and as strong as possible intensities. As the participant produced the vowel / ϵ / in ascending and descending glissando, the graph was marked with dots that corresponded to the frequency (abscissa) and intensity (ordinate) of the vocal productions. The participants were asked to emit the loudest possible tone during the vocal productions of glissando. The assessment of diadochokinesis was performed by counting peaks per second in the spectrogram, excluding the initial and final two seconds for analysis. For the analysis of acoustic parameters, the recording of the vowel / ϵ / was edited by discarding the first and last minutes of emission (as these segments showed greater instability), considering approximately three seconds of emission for analysis. The assessment of diadochokinesis was performed by counting peaks per second in the spectrogram, excluding the initial and final two seconds for analysis.

Statistical Analysis

The sample size was determined using the Sample Size Calculators tool designed by David Schoenfeld with the support of the Massachusetts General Hospital - Mallinckrodt General Clinical Research Center (http://hedwig.mgh.harvard.edu/sample_size/js/js_crossover_quant.html).

The calculation was carried out with 12 volunteers, considering the minimum detectable difference ($MDD: 1.96StandardError\sqrt{2}$) and the standard deviation of the primary outcome measures. A statistical power (β) of 80% and a significance level (α) of 5% were considered.

For data analysis, normality was tested using the Shapiro-Wilk test. To compare pre and post stimulation results, the Student's t-test was applied for parametric data and the Wilcoxon signed-rank test for non-parametric data. To compare the effects of tDCS across different time points, a Friedman ANOVA for repeated measures was conducted, followed by pairwise post hoc comparisons with a significance level of 5% ($p < 0.05$). All analyses were performed in SPSS software (version 26.0, SPSS Inc, Chicago, USA).

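### Does leaving open which glissando sets the vocal-effort note call for a change to the plan?

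*Combined protocol and SAP*

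**What the plan says.** All of this stands in the Study protocol section of the combined protocol and SAP unless noted otherwise.

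- Design: "the volunteers underwent four experimental sessions", one stimulation target in each.
- Timing: "The vocal assessment analysis was performed immediately before and after tDCS". The sentence just before it is narrower and says that "volunteers were systematically evaluated for vocal acoustic parameters and laryngeal diadochokinesis" around each session.
- Task (iv): "Pitch range assessment through ascending and descending glissandos up to the maximum vocal extension in weak and strong emissions".
- Task (v), next in the same list: "For phase 1, participants were asked to reproduce a note using a virtual keyboard", the note being placed "3 tones below their maximum glissando frequency". The effort rating follows at once. No second phase is described.
- Statistical Analysis section: "To compare pre and post stimulation results", a t-test or a Wilcoxon signed-rank test is used, and a Friedman test is added for time points. No covariate is mentioned, and neither is the pitch of the effort note.

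**The concern.** The effort note is defined by a person's maximum glissando frequency. That maximum is measured by another task in the same battery, and stimulation might change it. Three rules fit the wording: one note per participant, one per session, or one per assessment. The choice between weak and strong glissando is also open.

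Suppose the maximum rises after stimulation and the effort rating stays the same. With a kept note, the person spent equal effort on the same pitch, which now lies lower in the range. With a re-set note, the person spent equal effort on a higher pitch. One number then supports two different statements. What is at stake is the meaning of the effort result. The acoustic, cepstral and diadochokinesis results do not depend on this note.

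Two smaller features add to the doubt: the narrow sentence about what was evaluated around each session, and the label of a first phase with no later one.

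**Working it through.** The plan states no figure on this point, so there is none to reproduce. The check has three parts.

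**1. What the text settles.** The timing sentence covers the vocal assessment as a whole, and tasks (i) to (v) are then listed without exception. That tasks (iv) and (v) were done both before and after stimulation is therefore a reasonable reading. The narrower sentence is a summary and excludes nothing. The glissando comes directly before the effort task in the list, so the plainest reading is that the note came from the glissando just performed. This is not stated outright.

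**2. How many rules remain.** Possible settings of the note per participant:

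- at every assessment: 4 sessions × 2 = 8
- once per session: 4
- once per participant: 1

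For the pre-post comparison within a session these reduce to two cases. Under the last two rules the note is the same before and after; under the first it can move. The difference between 4 settings and 1 matters only when sessions are compared.

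**3. How far the two cases differ in pitch.** Assumptions, not in the documents: three tones equal 6 semitones in equal temperament, and the maximum shifts by k semitones within a session.

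- Re-set note: note / current maximum = 2^(-6/12) = 0.707 for any k. The note moves by 2^(k/12) - 1.
- Kept note: it does not move. Note / current maximum = 2^(-(6+k)/12).

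| k | Re-set note moves by | Re-set note, share of current maximum | Kept note, share of current maximum |
|---|---|---|---|
| -2 | -10.9% | 70.7% | 79.4% |
| -1 | -5.6% | 70.7% | 74.9% |
| 0 | 0 | 70.7% | 70.7% |
| +1 | +5.9% | 70.7% | 66.7% |
| +2 | +12.2% | 70.7% | 63.0% |

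Each rule holds one thing constant and lets another vary. A kept note fixes the pitch and lets its place in the range move; a re-set note does the reverse. At k = 0 they agree. The percentages only restate the definition of a semitone under assumed shifts. They are not evidence that the maximum moved.

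Going further to rating points needs a slope that the documents do not give. With an assumed 0.25 to 1.0 points per semitone and a gain of 2 semitones, the two rules differ by 2 × 0.25 = 0.5 to 2 × 1.0 = 2.0 points. If effort depends only on distance from the maximum, the kept note shows a fall of that size and the re-set note shows none. If effort depends only on absolute pitch, the kept note shows no change and the re-set note shows a rise of that size. Both the size and the direction of any change thus come from the assumptions.

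**The case for a change.** The strongest case for action is that the two rules are not equivalent for a pre-post comparison. A re-set note ties the task to something measured after stimulation. An unadjusted paired test on the rating would then mix a change in effort with a change in task difficulty, and a real benefit could be hidden or look like harm. The same would hold across targets if the note differed between sessions. It is also fair to say that effort cannot be dismissed as a secondary matter, because the Statistical Analysis section names no primary outcome at all.

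Part of this stands. If the note was re-set, the result is effort at a constant relative pitch, and it would be wrong to report it as effort on the same task. It also stands that the weak or strong glissando is not specified, so the maximum is not fully defined even within one assessment.

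The rest is conditional. The text does not say that the note was re-set, so a validity flaw cannot be read from it. Nor does a re-set note make the rating meaningless: it answers a different question that can be named. The label of a first phase is loose wording, with no consequence shown for any result.

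**Conclusion.** The detail is missing, but no change to the plan follows. The text does not show that a wrong rule was used. Both rules yield an interpretable effort comparison, and the planned paired test is the same under each. The description is in the past tense, so what is missing is a record of what was done. The investigators who set the notes can supply it when they describe the task, and can word the effort result to match.

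The scope is one of five tasks. No size in rating points can be drawn from the documents. The pitch differences shown, up to about 12% in frequency, rest on an assumed shift of up to 2 semitones and vanish if the maximum did not move within the session. The conclusion assumes that the same rule and the same type of glissando were used throughout. Nothing in the documents contradicts that, though it is not stated.

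### Blinding hides the stimulation target but not the time point, and no pre/post masking is described for peak counting or vowel trimming, so a reading lean would enter the pre/post tests

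*Combined protocol and SAP*

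**What the plan says.** **Blinding (Study protocol).** An external researcher prepares a counterbalanced session order, "to ensure blinding of both volunteer and therapist during vocal assessment". The allocation is kept in envelopes "accessible only to the researcher responsible for tDCS". What is concealed is the target for each session.

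**Timing and tools (Study protocol).** "The vocal assessment analysis was performed immediately before and after tDCS using the Voxmetria and Vocalgrama software from CTS Informatics".

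**Diadochokinesis (Study protocol).** The task is "rapid and interrupted repetitions of each vowel as fast as possible for eight seconds". The assessment is "performed by counting peaks per second in the spectrogram", with the first and last 2 s left out. No criterion for a peak is given. The plan does not say who counts, or whether software does.

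**Vowel recordings (Study protocol).** Both ends of the emission are discarded, "considering approximately three seconds of emission for analysis". The task lasts 5 seconds, so the word minutes in the trimming rule is probably a slip for seconds. The editor and the method are not stated.

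**Analysis (Statistical Analysis).** "To compare pre and post stimulation results", a t-test or a Wilcoxon signed-rank test is used. A Friedman analysis with pairwise follow-up tests is also planned. The four conditions are all active targets, with no sham session.

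**The concern.** Time point is not part of the allocation, so concealing the allocation cannot conceal it. Someone who assesses a volunteer around a stimulation session knows which assessment is the later one. If that person, or anyone else who can see the time point, counts peaks, an expectation of improvement can tilt doubtful peaks in the later recording. No coding, shuffling or masked reading is described that would prevent this.

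The pre/post tests have no other protection. With a sham session, a reading lean common to all sessions could be separated from a stimulation effect. With four active sessions it cannot. At stake is a reported vocal change after stimulation that reflects, in part or in whole, how the recordings were read.

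**Working it through.** **1. Does the described blinding reach the tested contrast?**

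| Comparison | Covered by target blinding? | Effect of a reading lean |
|---|---|---|
| Pre versus post within a target | No | Enters directly |
| Change compared between targets | Yes | Largely cancels if equal across targets |

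The second row helps only if the Friedman analysis compares changes between targets. The Statistical Analysis section describes it in terms of time points and does not say that change scores are compared.

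**2. Where is there room for discretion?** The counting window is fixed by rule, but what counts as a peak is not. For the vowel, keeping about 3 s of a 5 s emission after cutting both ends leaves little choice of segment. The exposure is therefore mainly in the count.

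**3. What is one peak worth?** The task lasts 8 s and the first and last 2 s are dropped: 8 − 2 − 2 = 4 s. One peak is 1/4 = 0.25 peaks/s, and half a peak is 0.125 peaks/s.

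**4. Illustrative effect on the false-positive rate.** The plan gives no figure to reproduce here: it reports no SD, no numerical detectable difference and no named primary outcome.

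Inputs:
- Two-sided test at 5%. The level is in the Statistical Analysis section; sidedness is assumed.
- n = 12. This is the number in the sample size paragraph, which does not make clear whether it is the planned sample or the data behind the calculation.
- SD of the paired change: 0.5 to 1.0 peaks/s (assumed).
- Mean lean, post minus pre: 0.125 to 0.25 peaks/s (assumed).
- True change: zero.

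Formula: the paired t statistic follows a noncentral t with df = 12 − 1 = 11 and noncentrality δ = (lean / SD) × √12. The false-positive rate is the probability that |t| exceeds the two-sided 5% critical value on 11 df.

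| Lean (peaks/s) | SD (peaks/s) | lean/SD | δ | False-positive rate |
|---|---|---|---|---|
| 0 | any | 0 | 0 | 5.0% |
| 0.125 | 1.0 | 0.125 | 0.43 | 6.8% |
| 0.125 | 0.75 | 0.167 | 0.58 | 8.3% |
| 0.125 | 0.5 | 0.25 | 0.87 | 12.4% |
| 0.25 | 1.0 | 0.25 | 0.87 | 12.4% |
| 0.25 | 0.75 | 0.333 | 1.15 | 18.4% |
| 0.25 | 0.5 | 0.5 | 1.73 | 35.3% |

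These rates are per test and for the t-test. The vowel-trimming route has not been quantified.

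**The case against.** A reader might infer that peaks were counted and recordings edited by hand by an unmasked therapist. The documents do not say that. They name analysis software and do not identify who counts or edits. Manual counting in a spectrogram is plausible, but it remains an inference. What can be said is that no masking is described and no automation is stated. This objection stands, and the point is worded accordingly.

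A reader might also infer that the trial's comparisons as a whole are compromised. That goes too far. Pre versus post is one of two planned analyses, and target blinding gives some protection to any between-target comparison. Peak counts are one outcome among several, and none is named as primary. This also stands, but it does not help the pre/post tests.

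The trimming rules limit choice of segment. That stands too, and it moves the weight of the concern to the count.

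Finally, the size depends on an assumed SD, lean and n. The 35% figure needs a mean lean of a full peak together with the smallest SD considered. At the other end the rate is about 7%, close to nominal. The documents do not show which end applies. The figures show sensitivity to a lean, not that one occurred.

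**Conclusion.** The point holds as a gap in protection. Whoever reads the recordings may know the time point, the plan describes nothing to prevent it, and the pre/post contrast is formally tested with no sham to absorb a lean. That conclusion follows from the text and does not depend on the arithmetic.

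The size is illustrative: about 7% to 35% per test instead of 5%, for a mean lean of half a peak to one peak, with n = 12 and an SD of change of 0.5 to 1.0 peaks/s. If counting and trimming are fully automated with fixed settings, the concern largely falls away.

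**What to change.** The external researcher who already prepares the session order should store the recordings under random codes that mix sessions and pre/post. The same reader trims and counts from the coded files in one batch, and the codes are broken only after the values are locked. If both steps are fully automated, the plan should state this and fix the settings instead.

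The cost is file coding and a batch reading after collection, with no extra staff. The downside is that results are not available the same day. Because the procedure works on stored files, it can still be applied after collection if the recordings were kept.

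It has limits. It does not cover measures taken live, namely the vocal range profile and self-rated effort. Nor does it remove practice, fatigue or expectation effects from the uncontrolled pre/post contrast; it removes only the reader's contribution.

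### Do the vowel edit stated in minutes and the unqualified loudness instruction for glissandos require a change to the plan?

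*Combined protocol and SAP*

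**What the plan says.** All the relevant text is in the Study protocol section of the combined protocol and SAP.

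- **Vowel length.** In the list of vocal tasks, the sustained vowel for vocal quality (task i) is recorded "for 5 seconds at weak intensity (below 70dB" and again at habitual and strong intensity. Task (ii), the cepstral analysis, also uses a 5-second vowel.
- **Vowel editing.** The last paragraph before Statistical Analysis says that the recording "was edited by discarding the first and last minutes of emission", because the ends were less stable, "considering approximately three seconds of emission for analysis".
- **Diadochokinesis editing.** In the same paragraph, peaks are counted "excluding the initial and final two seconds for analysis". That task lasts eight seconds.
- **Glissandos.** Task (iv) asks for "ascending and descending glissandos up to the maximum vocal extension in weak and strong emissions". The vocal range profile description repeats this as "as weak as possible and as strong as possible intensities", and two sentences later adds: "The participants were asked to emit the loudest possible tone during the vocal productions of glissando".
- **Effort note.** In task (v) the participant holds a note "3 tones below their maximum glissando frequency" while counting, then gives a Borg rating.

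**The concern.** Read on its own, the vowel edit cannot be carried out: a 5-second recording has no minutes to discard. The edit fixes the window for every acoustic measure taken from the vowel, before and after stimulation at each of the four sites. If the trim were really unknown, a reader could not tell what was measured, and two analysts might cut differently.

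The loudness sentence raises a similar doubt. It is not limited to the strong glissandos, so read literally it conflicts with the request for the weakest possible voice. If participants had been asked for maximum loudness throughout, the lower intensity contour of the vocal range profile would not be what it claims to be.

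The effort note depends on a maximum frequency whose source is not named. If that maximum was re-measured after stimulation, the pre and post Borg ratings within a session may refer to different pitches.

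**Working it through.** **Vowel edit.** Inputs from the Study protocol section: recorded length 5 s (tasks i and ii); length kept about 3 s (editing sentence); discarded part given in minutes, without a number.

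Formula: length kept = recorded length - 2 x trim at each end.

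The plan's own figure is about 3 s. Solving for the trim: (5 - 3) / 2 = 1 s at each end. The alternatives are:

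| Trim at each end | Calculation | Length kept |
|---|---|---|
| 1 minute (literal, smallest reading) | 5 - 2 x 60 | -115 s |
| 0.5 s | 5 - 2 x 0.5 | 4 s |
| 1 s | 5 - 2 x 1 | 3 s |
| 1.5 s | 5 - 2 x 1.5 | 2 s |
| 2 s | 5 - 2 x 2 | 1 s |

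Of these, only one second reproduces the stated figure. To lose a minute at each end and still keep 3 s, the recording would have to last 2 x 60 + 3 = 123 s, which no task requests.

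The two-second trim belongs to diadochokinesis, where it works: 8 - 2 x 2 = 4 s. Nothing in the text applies it to the vowel, and the stated three seconds rules it out there.

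Reach of the rule: 3 intensities x 4 sessions x 2 assessments = 24 vowel recordings per volunteer, or 48 if tasks (i) and (ii) are recorded separately. This counts the recordings covered by the sentence. It is not evidence that any of them was edited wrongly.

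**Glissandos.** There are 2 directions x 2 intensities = 4 conditions, of which 2 are weak. Set side by side:

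- Task (iv) names weak and strong emissions.
- The vocal range profile opens by naming the weakest and strongest possible intensities.
- The later sentence asks for maximum loudness and names no condition.

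If the later sentence governs all glissandos, it contradicts 2 of the 4 conditions and cancels two explicit statements. If it elaborates the strong condition, it contradicts none. The weak contour rests on the wording that asks for it, and that wording is clear.

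**Effort note.** Any of the four glissando conditions could supply the maximum, at either assessment. A note fixed in pitch asks how hard the same tone feels before and after. A note set relative to the current maximum asks how hard a tone at the same distance below that maximum feels. The documents give no ground for preferring one, and no direction of bias follows from either.

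**The case for a change.** The best argument for a change is that a public protocol should contain rules that can be followed as printed, and this one does not. The text itself says the ends of the vowel are unstable, so the window matters to the sponsor. Replacing minutes with seconds, without a number, would leave the trim unstated, while a neighbouring rule uses two. The repair costs a few words, and a person repeating the procedure should not have to infer which glissandos were meant to be loud.

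Part of this stands. The unit is wrong, the loudness sentence lacks a qualifier, and the source of the effort note is unstated. The argument does not establish that the vowel rule cannot be followed. Whoever edits a 5-second recording can keep the central three seconds or so, and the remaining looseness comes from the plan's own word for approximately. Nor does it show that the loudness sentence overrides the weak condition. On the effort note it identifies missing detail, not a contradiction.

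**Conclusion.** No change to the plan follows. The vowel edit contains a definite slip of unit, and the correct reading is recoverable from the 5 seconds recorded and the three seconds kept: about one second at each end. The loudness sentence is loosely worded, and two explicit statements protect the weak glissandos. The effort note is a detail that can be reported either way.

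The effect on sample size, significance level, power and the planned comparisons is nil, since none of them uses these figures.

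The conclusion assumes that the stated length kept describes what was done and that the trim was roughly equal at both ends. It also assumes that the loudness sentence refers to the strong emissions, which is probable from context but not stated. The account is written in the past tense, so the text can only be brought into line with what was done. The sponsor could confirm the trim and correct the unit, add the qualifier if it is accurate, and say which note was used in the effort task. These are editorial points and alter nothing that the trial does or concludes.

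### With four active targets and no sham, a significant pre-post test cannot be attributed to tDCS, and the plan does not say whether its Friedman test compares targets

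*Combined protocol and SAP*

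**What the plan says.** The title sets the question as "Effect of Transcranial Direct Current Stimulation on the Voice". The Study protocol section describes a crossover of four sessions, each stimulating one target: "i) left laryngeal M1, (ii) left S1 of the larynx, (iii) left DLPFC, and (iv) cerebellum". One stimulation setting is given (2 mA for 20 minutes), and no sham, no-stimulation or time-only session is listed.

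On timing: "The vocal assessment analysis was performed immediately before and after tDCS". The tasks include maximal glissandos, vowel repetition at top speed and a self-rated effort score.

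The Statistical Analysis section has two parts that matter here:

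- a t-test or Wilcoxon signed-rank test "To compare pre and post stimulation results";
- a second analysis: "To compare the effects of tDCS across different time points, a Friedman ANOVA for repeated measures was conducted", followed by pairwise comparisons at 5%, with no adjustment stated.

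It defines no change score, does not list the columns that enter the Friedman test, and does not say which analysis carries the conclusion.

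**The concern.** A pre-post difference within an active session is the sum of any tDCS effect and whatever else happens between the two recordings: repeating effort-dependent tasks, warming up or tiring, sitting for 20 minutes, and expecting a result. Without a sham or time-only session, the pre-post test cannot separate these.

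The plan's safeguards act elsewhere. Counterbalanced random order and the washout deal with order and carry-over between sessions. Sealed envelopes, and procedures "to ensure blinding of both volunteer and therapist during vocal assessment", protect the comparison of one target with another. None of them removes a change that occurs inside every session.

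Two wrong conclusions are at stake. One is that tDCS changed the voice when drift alone did. The other is that some targets work and others do not, because some pre-post tests passed 5% and others missed it. The only protection against either is a direct comparison between targets, and the Friedman sentence is too vague to show that one is planned.

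**Working it through.** **Inputs.** From the documents: four active sessions, one recording before and one after each, α = 5% (two-sided assumed), and "The calculation was carried out with 12 volunteers". I take 12 as the number analysed; no final number is stated. The documents give no SD, drift or correlation, so these are assumed and varied. For the same reason the sample size of 12 cannot be reproduced, and the argument does not depend on it.

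**Why drift cancels in one analysis and not the other.** Write the change for a volunteer at target j as τ_j + d + error, where τ_j is the tDCS effect and d the drift common to all sessions. The pre-post test examines τ_j + d. A contrast of targets j and k examines τ_j − τ_k, and d drops out.

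**Pre-post test with no tDCS effect.** With drift expressed in SDs of the change, the noncentrality is drift × √12 on 11 degrees of freedom, and the two-sided critical value is 2.201.

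| Drift (SD) | Noncentrality | One test significant | At least one of four, independent | At least one of four, correlation 0.5 |
|---|---|---|---|---|
| 0 | 0 | 5% | 19% | about 16% |
| 0.3 | 1.04 | 16% | 50% | 39% |
| 0.5 | 1.73 | 35% | 82% | 67% |
| 0.8 | 2.77 | 71% | 99% | 94% |

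The independent column is 1 − (1 − p)⁴; at drift 0.3 that is 1 − (1 − 0.158)⁴ = 0.498. The last column is simulated. The zero-drift row is multiplicity alone; the rise below it is due to drift.

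**Friedman test with no tDCS effect** (simulated, chi-square reference; w is the pre-post correlation within a session).

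| Columns ranked | Drift 0 | 0.3 | 0.5 | 0.8 |
|---|---|---|---|---|
| Four changes, or four post values | 4–5% | 4–5% | 4–5% | 4–5% |
| Eight mixed, w = 0 | 4% | 20% | 57% | 96% |
| Eight mixed, w = 0.5 | 5% | 13% | 33% | 83% |
| Eight mixed, w = 0.8 | 7% | 10% | 18% | 48% |

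**A split across targets is not site specificity.** Suppose all four targets share one true effect of 0.889 SD, which gives 80% power per test. With independent changes, the results split into significant and non-significant in 1 − 0.8⁴ − 0.2⁴ = 1 − 0.4096 − 0.0016 = 59% of trials. Simulation gives 43% at correlation 0.5 and 34% at 0.7.

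**What a between-target test does not remove.** For the cerebellum, "the anode was placed over inion and the cathode over the right deltoid muscle"; the other three montages put the cathode over the supraorbital region. If one montage alone carries a non-specific shift of 0.3, 0.5 or 0.8 SD, Friedman on the changes rejects 8%, 15% or 34% of the time with independent changes, and 12%, 27% or 63% at correlation 0.5.

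**The case against.** The plan states no hypothesis or decision rule, so the claim that pre-post tests would be credited to tDCS is inferred from the title. Pre versus post is already assigned to the t-test or Wilcoxon test and each session has only two recordings, so a separate Friedman test must span sessions. Its natural reading is a comparison of the four targets, which cancels common drift. The drift sizes are assumed; practice and fatigue may offset each other, and at 0.1 or 0.2 SD one pre-post test rejects only about 6% or 10% of the time. The figures for at least one of four include multiplicity, and an omnibus rejection on eight columns is not in itself a claim about tDCS.

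Much of this is fair as a limit on size. The percentages are illustrative, and small net drift does little harm. It does not restore the pre-post test, which has no comparator at any drift. Nor does the charitable reading settle the Friedman wording: the text speaks of time points, not targets, and could also mean sessions in calendar order, which would test period. The absence of a decision rule is part of the problem, because nothing stops the uncontrolled test from carrying the conclusion.

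Two further remarks stand as refinements. The plan mentions primary outcome measures without naming them, so they must be named before any fix can be applied. A baseline-adjusted model would avoid the choice between changes and post values.

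**Conclusion.** The concern holds. The explicit pre-post test cannot answer the title question, and the analysis that could support a relative claim is not specified. The structural point needs no numerical assumption: drift common to all sessions stays in every pre-post difference and cancels only between targets.

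The size is conditional on 12 volunteers analysed, additive drift common to all targets and no tDCS effect. At a drift of half an SD of the change, a pre-post test is significant 35% of the time, against 4–5% for Friedman on the changes and 18–57% for Friedman on mixed columns. Even a sound between-target result shows only that active targets differ from one another. Where the cerebellar montage is involved, the difference may also reflect sensation or expectation.

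**What to change.** Name the primary outcomes, then amend the Statistical Analysis section as follows.

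1. State that inference for each primary outcome rests on the four pre-to-post changes, by Friedman test or a repeated-measures model, with Holm adjustment over the six pairwise target contrasts. State that pre and post columns are not mixed in one Friedman test.
2. Report within-target pre-post changes as estimates with 95% confidence intervals, not as evidence of a tDCS effect.
3. Word conclusions as differences between active targets. Say that an absolute tDCS effect cannot be claimed without sham, and that contrasts with the cerebellar montage may reflect sensation or expectation.

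This changes analysis text and conclusion wording only; it needs no extra session, volunteer or measurement. The cost is a narrower claim and less power. For a 0.8 SD difference between two targets with 12 volunteers, the standardised contrast is 0.8/√(2(1 − ρ)), where ρ is the correlation of changes: 0.57 at ρ = 0 and 0.80 at ρ = 0.5.

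| Power for one contrast | ρ = 0 | ρ = 0.5 |
|---|---|---|
| Unadjusted | 43% | 71% |
| Bonferroni over six (lower bound for Holm) | 16.5% | 38% |
| Holm, one target differing from the other three | 18% | 41% |

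Changes also lose power to post values when w is below 0.5. With one target shifted by 0.8 SD and independent changes, Friedman power is 34% on changes against 63% on post values at w = 0, equal at w = 0.5, and 34% against 15% at w = 0.8. A baseline-adjusted repeated-measures model is a reasonable alternative. With power this low, null contrasts should be reported with confidence intervals and not read as equivalence.
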